Appendix

## **1. Background Information and Rationale**

### **1.1 Introduction**

Emergency surgical interventions represent stressful and difficult decisions for patients and caregivers. Approximately 136 million Americans seek emergency medical care each year with over 3.4 million people being evaluated for the diagnosis of abdominal pain. Appendectomy is the most common emergency operation performed for abdominal pain in both adults and children. Nonoperative management of appendicitis with antibiotics alone has emerged as a viable treatment alternative to appendectomy. Despite the extensive costs and morbidity of emergency surgery, as well as uncertainties about treatment, there is little evidence examining the effects of patient activation on decision making and patient centered outcomes in the emergency care setting. We propose a randomized controlled trial (RCT) of standard surgical consultation alone compared to standard surgical consultation plus a patient activation tool (PAT) in patients choosing operative or non-operative therapy for appendicitis. Our goal is to determine if a PAT can improve decision making and patient centered outcomes in pediatric patients with appendicitis and their caregivers.

### **1.2 Relevant Literature and Data**

According to the U.S. Department of Defense Patient Safety Program, there are three essential components of patient activation: establishing patients' willingness to take an active role in their care, ensuring patients' confidence in their ability to manage their care, and providing patients with the knowledge and skills necessary to make decisions and manage their own care. In adult patients, patient activation has been shown to improve healthy behaviors, increase the appropriate use of healthcare resources, improve patient preparedness for medical appointments, and improve the management and control of chronic illnesses such as diabetes. There is little evidence examining patient activation on decision making and patient centered outcomes in the emergency care setting, or in pediatric surgery.

Emergency surgical interventions present stressful and difficult decisions for patients and caregivers. Surgeons provide generalized information about treatment options to acutely ill patients and time for shared decision making is limited. This is especially true in vulnerable populations such as children, in which caregivers are forced to take in large amounts of information and make quick decisions for someone other than themselves. We hypothesize that strategies to activate caregivers in the emergency setting through knowledge and engagement may result in improved decision making with improved self-efficacy and confidence. This could lead to improvements in other patient centered outcomes such as health related quality of life and healthcare satisfaction for both the caregiver and the pediatric patient. In this study, we define an activated patient-caregiver dyad primarily on the willingness, knowledge, engagement, and self-efficacy of the caregiver.

Our study has the potential to significantly alter patient health, well-being, and the quality of care that patients receive in four ways: First, patient activation in *pediatric* patient-caregiver dyads will be examined. The majority of studies on patient activation, decision making, and patient centered outcomes focus on autonomous adult patients. However, the role of the caregiver is crucial in all of pediatric medicine. Despite this, there are few studies that examine patient-caregiver dyads in the context of clinical decision making and even fewer that study children. Second, this study focuses on patient activation in the emergency care setting. Most research on patient activation, decision making, and patient centered outcomes is focused on chronic illness and/or outpatient care. Third, this study investigates the effects of patient activation on decision making and patient centered outcomes in a surgical disease. Several studies investigating the ability of decision aids to improve patient knowledge, one component of activation, have been performed in patients undergoing major elective surgery. However, none of these studies targeted emergency surgical procedures or children. Results from our study will provide information on the utility of a PAT to facilitate patient-caregiver dyad activation in emergency surgical interventions and in children. Fourth, this study will use a multi-media patient activation

tool that incorporates patient activation strategies with a decision aid. While traditional paper-based tools and multi-media tools may contain identical information, the use of a multi-media tool offers the advantage of customization, feedback, and greater visual features. In addition, multimedia has the added benefit of motivating participants to learn topics that they would usually avoid and obtain information they would not seek out from traditional sources. Furthermore, the PAT incorporates interactive technology designed to promote patient activation, improve decision making, and effectively communicate and resolve uncertainty, in addition to eliciting rapid understanding of the disease and treatment options.

We are currently performing a pilot study offering nonoperative management as a treatment choice to patients and their caregivers. Thus far, 80% of children initially treated non-operatively did not require appendectomy, and no patients have had an adverse event or progressed in disease severity. We believe that both non-operative management and appendectomy are safe and effective treatment options for early appendicitis. As such, we are beginning to offer antibiotic therapy as an alternative treatment option to patients outside those participating in the pilot study. Although we believe we have enrolled a sufficient number of patients to determine that non-operative management is safe, we are continuing to enroll patients in the pilot study in order to more precisely determine the recurrence rate.

However, determining the best treatment requires engaging the patient and caregiver in the treatment decision. During the study, caregivers reported difficulties to our research team in understanding the treatment choices and determining which treatment choice was best for them. A previous study by our group ([name]) demonstrated that a computerized parent education tool improved knowledge about appendicitis in parents giving informed consent for their child to undergo appendectomy. This study demonstrated the potential value of using computerized tools in the emergency surgical setting to provide information to parents about the care of their child. We hypothesize that an interactive PAT that activates and informs the child and the caregiver will lead to more willing, confident, and informed treatment choices in pediatric patients with early appendicitis and their caregivers. This activation process is expected to improve measures of decision making and patient-centered outcomes without compromising medical outcomes.

To our knowledge, this will be the first study to combine a patient activation strategy with a decision aid for patient-caregiver dyads in the emergency surgical setting. Results from this study will be informative about the utility of patient activation in this setting. A positive result from our study could lead to the rapid development of PATs for appendicitis at the majority of children's hospitals in the United States and Canada. In addition, because the underlying structure of the PAT is modular, it can be adapted and studied for use in other emergency and urgent surgical procedures in both children and adults.

## **2. Study Objectives**

### **2.1 Primary Objective**

Phase 1 Primary Objective: To develop an interactive PAT that will engage both parent and child in learning about appendicitis and activating the family with an expectation of improving decision making and patient-centered outcomes.

Phase 2 Primary Objective: After development of the PAT, to perform a randomized controlled trial to determine if a patient activation tool (PAT) can improve decision making and patient centered outcomes in pediatric patients with appendicitis and their caregivers, as compared to standard surgical consultation.

## 2.2 Secondary Objective

The secondary objective is to characterize the effects of a PAT on medical outcomes from appendicitis in patients receiving the PAT compared to those receiving standard surgical consultation alone. We will determine differences in disability days, length of stay, readmission rates, and medical complications related to treatment choice (e.g. infection, recurrence).

## **3. Investigational Plan**

### 3.1 Study Design

This study will be performed in two phases.

#### *Phase 1:*

We will develop the interactive PAT in collaboration with software developers, computer scientists, and communication experts to ensure that the PAT is designed in a manner that will engage and activate patients and caregivers.

The PAT will be designed to encourage active involvement in the treatment choice, outline the two treatment options with the attendant risks and benefits, elucidate the caregiver's values and decisional support, and teach patient-caregiver dyads how to communicate decisional uncertainty.

#### *Phase 2:*

After the development of a PAT, we will conduct a prospective, single-blind, single-site, randomized trial to determine if providing patient-caregiver dyads with a PAT improves decision making and patient centered outcomes without compromising medical outcomes compared to standard surgical consultation alone in pediatric patients (7-17 years old) with early appendicitis and their caregivers. The patient-caregiver dyads and the physician research members administering the PAT will not be blinded. All clinicians subsequently interacting with these patients will be blinded as to whether the patient received the PAT or not.

### 3.2 Study Duration and Enrollment

#### *Phase 2:*

##### 3.2.1 Duration of Study and Enrollment

This study will be conducted for at least 3 years with follow-up phone calls at 30 days, 6 months and 1 year, then annually for 3 years. At the conclusion of the 3 year period, for the subjects who have chosen non-operative management, an annual follow-up will be conducted.. A minimum of 3 year's data will be necessary to collect.

##### 3.2.2. Total Number of Subjects Projected and Site

A total of 200 patient-caregiver dyads (100 in each arm) are projected to be enrolled. The study will be conducted at Nationwide Children's Hospital (NCH). Eligible patients will be recruited and consented during their initial surgical evaluation in the emergency department.

Follow-up research visits will be conducted either by phone, email, at the outpatient surgical center of Nationwide Children's Hospital (NCH), or at the Center for Surgical Outcomes Research (CSOR) within the

### 3.3. Study Population

Children between the ages of 7-17 who are diagnosed with early appendicitis will be screened for eligibility.

#### 3.3.1 Inclusion Criteria

- Age : 7-17 years
- US or CT confirmed early appendicitis:
  - US: hyperemia,  $\leq 1.1$  cm in diameter, compressible or non-compressible, no abscess, no fecalith, no phlegmon
  - CT: hyperemia, fat stranding,  $\leq 1.1$  cm in diameter, no abscess, no fecalith, no phlegmon
- WBC  $< 18, > 5$
- Focal abdominal pain  $\leq 48$  hours prior to receiving antibiotics

#### 3.3.2 Exclusion Criteria

- Positive urine pregnancy test
- Diffuse peritonitis
- History of chronic intermittent abdominal pain

### 4. Study Procedures

This study will be performed in two phases.

#### Phase 1:

Develop the PAT in collaboration with software developers, computer scientists, and communication experts.

This will be an interactive program that will allow patients to choose an avatar who will guide them through an educational program. This will be designed for both the patient (child) and caregiver, and is meant to present information about their condition (acute appendicitis) and the treatment options (appendectomy or antibiotics). In addition to providing information regarding appendicitis and the two treatment options, the PAT will include two separate brief video clips that encourage active involvement in the treatment choice and teach patient-caregiver dyads how to communicate decisional uncertainty.

#### Phase 2: (Target start date 3/1/14)

##### Screening and Enrollment

All children age 7-17 years with a diagnosis of early appendicitis treated at NCH will be screened for study eligibility. Once eligibility is confirmed, and consent obtained, the patient-caregiver dyad is randomized to either a standard surgical consultation (control arm) or to a surgical consultation plus the PAT (intervention arm) by physician research members trained to perform both types of consultations. The consultations will occur in the NCH Emergency Department or one of the inpatient units at NCH. They will then be consented and consultation will commence.

##### Study Procedures:

### Consultation

All randomized patients will be approached by a trained physician research member who will conduct the consultation prior to meeting the surgeon.

Patient-caregiver dyads randomized to the standard consultation will receive only verbal information regarding the two treatment options (operative or non-operative management) with patients having the opportunity to ask questions. This type of consultation is akin to a typical surgical consultation in which surgeons verbally inform patients of their options and elicit questions.

A trained physician research member will administer the PAT among patient-caregiver dyads randomized to the PAT and then answer questions about the risks and benefits of each treatment option. If the child is in 5th grade or higher, they will have the option of having their own tablet to watch the PAT.

After the physician research member has answered all patient and caregiver questions, the patient-caregiver dyad will choose either appendectomy or non-operative management. Discrepancies between the caregiver's choice and the patient's choice will be recorded, but the caregiver, by law, will make the decision. Both arms will complete computer-based questionnaires that measure patient and caregiver recall, caregiver activation, preparedness for decision making, decision self-efficacy, and decisional conflict after the treatment choice has been made. Any patient or caregiver who wishes to speak with a member of the surgical team prior to making a decision will be able to do so.

The physician research member will then inform the clinical team of the treatment choice and the surgeon will be called to speak with the family for a full discussion of the care plan and to obtain surgical consent if operative management was chosen.

The patient will be admitted to the hospital and receive care according to standard protocols for either appendectomy or non-operative management of appendicitis. Based on the results of our pilot study, we have demonstrated that non-operative management is a reasonable alternative to appendectomy for cases of early, acute appendicitis. As such, we are presenting both options as initial treatment options for early acute appendicitis to patients and their caregivers.

Before discharge, the patient and legal guardian will complete another set of questionnaires that measure: the patient's quality of life (QOL), caregiver satisfaction of care received, decision self-efficacy, decisional regret, reasons for initial choice and general socioeconomic status (SES) information. We will give English-speaking participants and families the option of conducting follow-ups via phone call and/or email. The emails will be sent from REDCap to ensure security.

A follow-up reminder letter will be mailed/ emailed/texted to all families to reiterate follow-up time points.

### Follow-Up

#### Participants who choose non-operative management

##### 2-5 days and 10-14 days

A member of the research team will call and/or email the family for a follow-up. Any concerns, issues or complications regarding the oral antibiotics or the study will be discussed. In addition, how many days the child missed at school and the legal guardian missed at work will also be assessed.

## All participants

### 30 ( $\pm 10$ ) days

Depending on the child and legal guardian's preference, they will either return to NCH or a member of the research team will call or email the family for a follow-up. In addition, if they have already scheduled a follow-up appointment with their surgeon, we will attempt to schedule our appointment during the same day. The child and legal guardian will complete another set of questionnaires that measure: the patient's quality of life (QOL), caregiver satisfaction of care received, decision self-efficacy, decisional regret, satisfaction with decision and patient and caregiver recall (if patient is in the 5th grade or higher and they were given their own tablet to watch the PAT).

We will also ask questions about any problems the child has had, dependent on the treatment option, with their appendix or surgery since discharge, any other issues, and how many days the child missed school and the legal guardian missed work and any out-of-pocket expenditures (e.g. insurance copayments, and outpatient medications). This will be conducted either in person, over the phone or email. A \$25 VISA® ClinCard will be provided. If the child and legal guardian prefer a phone or email follow-up, the gift card will be mailed to the legal guardian's address. A parking voucher will be provided if they decide to come back to NCH for their 30 day follow-up.

Data will also be collected from additional chart review and claims data. This will include: appendicitis recurrence with determination of simple vs. complicated appendicitis from operative and pathology reports; subsequent ED visits or physician visits; subsequent readmissions and reoperations; additional imaging, pharmaceutical, and laboratory procedures related to their chosen appendicitis treatment, if any.

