## **5. Statistical Considerations**

### 5.1. Primary and Secondary Endpoints

#### Patient Centered

Primary patient centered endpoints are decision self-efficacy immediately after the patient and caregiver have made their decision regarding operative or non-operative treatment (within one hour of the decision) and healthcare satisfaction at discharge.

Secondary patient centered endpoints are preparedness for decision making and caregiver activation level immediately after the patient and caregiver have made their decision, recall (knowledge) immediately after the patient and caregiver have made their decision and at 30 days follow-up, decision regret at discharge and 30 days follow-up, decisional conflict immediately after the patient and caregiver have made their decision, reasons for initial choice at discharge, satisfaction with decision and health care associated costs at 30 days and 1 year, and health related quality of life (HRQOL) prior to discharge and 30 days after discharge.

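### Children's recall at 30 days has no control group, because it is collected only from children who had their own tablet for the PAT

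*Protocol*

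**What the plan says.** Section 5.1 (Patient Centered) names as a secondary endpoint "recall (knowledge) immediately after the patient and caregiver have made their decision and at 30 days follow-up". It sets no limit by arm, grade or device.

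Section 4 gives the collection rules:

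- **Arms** (Screening and Enrollment). Dyads are randomised to a "standard surgical consultation (control arm) or to a surgical consultation plus the PAT (intervention arm").
- **Control consultation** (Consultation). "Patient-caregiver dyads randomized to the standard consultation will receive only verbal information regarding the two treatment options".
- **Tablet** (Consultation). In the paragraph on dyads randomised to the PAT, if the child is in 5th "grade or higher, they will have the option of having their own tablet to watch the PAT".
- **Recall after the decision** (Consultation). "Both arms will complete computer-based questionnaires that measure patient and caregiver recall". No grade or tablet condition applies.
- **Recall at 30 days** (All participants, 30 ± 10 days). The questionnaire list ends with "decisional regret, satisfaction with decision and patient and caregiver recall (if patient is in the" 5th "grade or higher and they were given their own tablet to watch the PAT").

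The 6-month, 1-year and annual contacts schedule no recall measure.

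**The concern.** The 30-day rule joins two conditions with 'and', and the second can be met in only one arm. A child who was never shown the PAT cannot have been given a tablet to watch it. The rule therefore removes every control child from an endpoint whose purpose, under the Phase 2 objective in section 2.1, is to compare the PAT with standard consultation.

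The children who remain are also selected. The tablet is an option taken up after randomisation, so those measured are the older PAT-arm children who accepted it. Their recall may differ from that of other PAT-arm children for reasons unrelated to the PAT.

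This is a rule about what is collected, so an analysis plan cannot repair it. Recall not measured in the 30-day window cannot be rebuilt from the chart review or claims data that the protocol also gathers.

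**Working it through.** The protocol states no sample size, power or effect size for recall, so there is no figure to reproduce. The main check is one of logic; the arithmetic only shows what the correction would give.

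**Step 1. Who can meet the 30-day condition?** The planned size is 100 dyads per arm (section 3.2.2: "A total of 200 patient-caregiver dyads (100 in each arm) are projected to be enrolled").

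| Measure at 30 days | Control | PAT arm |
|---|---|---|
| Child recall, either reading of the bracket | 0 of 100 | children in 5th grade or above who took a tablet |
| Caregiver recall, bracket covers the child only | up to 100 of 100 | up to 100 of 100 |
| Caregiver recall, bracket covers both | 0 of 100 | only caregivers whose child met both conditions |

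The zero for control children needs no assumption and does not depend on how the bracket is read.

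**Step 2. How many PAT-arm children remain?** The number is 100 × f × u, where f is the share in 5th grade or above and u is tablet uptake. The protocol gives neither, so both are assumptions.

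- f = 0.50 to 0.80. As a guide, ages 7 to 17 spread evenly over 11 years, with 5th grade starting at age 10 or 11, give 8/11 = 0.73 or 7/11 = 0.64.
- u = 0.25 to 1.00.
- Lowest: 100 × 0.50 × 0.25 = 12.5. Highest: 100 × 0.80 × 1.00 = 80.

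So about 12 to 80 PAT-arm children would be assessed, against 0 controls.

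**Step 3. What would be testable without the tablet condition?** With grade alone applied in both arms, n = 100 × f = 50 to 80 per arm. The detectable standardised difference at two-sided 0.05 and 80% power, with no dropout, is (1.960 + 0.842) × √(2/n) by the normal approximation. The t-test figures are slightly larger.

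| n per arm | Normal approximation | Two-sample t-test |
|---|---|---|
| 50 | 2.802 × √(2/50) = 0.560 | 0.566 |
| 80 | 2.802 × √(2/80) = 0.443 | 0.446 |
| 100 (all caregivers) | 2.802 × √(2/100) = 0.396 | 0.398 |

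As written, no difference in children's recall at 30 days can be tested, whatever its size.

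**The case against.** **The endpoint may mean caregiver recall.** Section 5.1 does not say whose recall is measured, and section 1.2 defines the activated dyad mainly through the caregiver. If the endpoint is caregiver recall and the bracket concerns only the child, the listed endpoint keeps both arms and only an additional child measure is lost. This limits the point but does not remove it: both recall instructions in section 4 name the patient as well as the caregiver, and the first collects both in both arms.

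**The bracket is most naturally about the child.** It speaks of the patient's grade and the patient's tablet, and there is no evident reason to tie a caregiver's recall to either. That is fair. The loss of control caregivers is therefore a risk of one reading, not an established consequence.

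**It may be a drafting slip.** The visit is headed as applying to all participants, so the clause may have been meant to screen out PAT-arm children who did not view the content themselves. Even so, it is the only instruction staff have for 30-day recall. Control children also hear both options explained, and their recall is measured after the decision, so the same questionnaire makes sense for them.

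**The edit may come late.** The text carries a date of February 2017 against a target start of March 2014, and section 5.3 implies about 100 enrolments a year (50% of just over 200). On those planned figures most 30-day contacts would be past. Actual accrual is not given, so this stands as a caution about what can still be recovered.

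**Conclusion.** The concern holds. Under the protocol's own rules, child recall at 30 days is collected from 0 of 100 control children and from a self-selected part of the PAT arm, so it gives no randomised comparison. That conclusion rests on the text alone. Whether caregiver recall is also lost depends on how the bracket is read; the child-only reading is the more natural one but is not stated. The counts of 12 to 80 PAT-arm children, and the 0.57 to 0.45 SD detectable after correction, rest on the assumed grade share and uptake and serve only to show scale.

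The consequence is limited to one timepoint of one secondary endpoint. Post-decision recall, the two primary patient-centered endpoints, disability days, the stated power and the Holm and fallback plan are untouched. It should be fixed, but it does not threaten the trial's main conclusions.

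**What to change.** In the 30-day section, remove the tablet condition and replace the bracket with a plain statement: the recall questionnaire goes to every caregiver in both arms, and to every child in 5th grade or above in both arms, whether or not a tablet was used. Leave post-decision recall as it is. It has no grade limit, so the two timepoints will cover different children unless the sponsor also drops the grade condition at 30 days. Either choice works, provided the rule is the same in both arms. Section 5.1 should say whose recall is the endpoint.

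The cost is one sentence in section 4, a clarification in section 5.1, and a few minutes of an existing questionnaire at a contact already planned for all participants. If 30-day contacts are already complete, the sponsor should report who was actually assessed in each arm and, if no control children were, should not present child recall at 30 days as a randomised comparison.
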